11.2.3 Listing of Adverse Events

The following listings of adverse events will be prepared:

- All serious adverse events (from the time the subject signed the study-specific informed consent through the end of the study),
- Treatment-emergent serious adverse events,
- Treatment-emergent adverse events leading to death,
- Treatment-emergent adverse events leading to discontinuation of study drug,
- Treatment-emergent adverse events leading to study drug interruption,
- Treatment-emergent adverse events leading to RBV dose modification (Arm B only).

11.3 Analysis of Laboratory Data

Data collected from the central and local laboratories, including additional laboratory testing due to an SAE, will be used in all analyses.

11.3.1 Variables and Criteria Defining Abnormality

Hematology variables include: hematocrit, hemoglobin, red blood cell (RBC) count, white blood cell (WBC) count, neutrophils, bands, lymphocytes, monocytes, basophils, eosinophils, platelet count, reticulocyte count, prothrombin time (PT), international normalized ratio (INR), and activated partial thromboplastin time (aPTT).

Chemistry variables include: blood urea nitrogen (BUN), creatinine, total bilirubin, direct and indirect bilirubin, alanine aminotransferase (ALT), aspartate aminotransferase (AST), alkaline phosphatase, sodium, potassium, calcium, inorganic phosphorus, uric acid, cholesterol, total protein, glucose, triglycerides, LDL, HDL, albumin, chloride, bicarbonate, magnesium, total insulin, gamma-glutamyl transferase (GGT), creatinine clearance (calculated using Cockcroft-Gault), and estimated glomerular filtration rate (eGFR) calculated using the modification of diet in renal disease (MDRD) equation defined below.

Urinalysis variables include: specific gravity, ketones, pH, protein, blood, glucose, urobilinogen, bilirubin, leukocyte esterase, and microscopic (reflex performed if other variables are abnormal).

Some of the above laboratory variables are calculated by the laboratory vendor including indirect bilirubin, creatinine clearance, and eGFR by MDRD. The central lab calculates eGFR by MDRD modified for Japanese population using the following equation, where serum creatinine is measured in mg/dL and age is measured in years:

$$eGFR_j \text{ (mL/min/1.73 m}^2\text{)} = 194 \times (\text{Serum Creatinine})^{-1.094} \times (\text{Age})^{-0.287} \times 0.739 \text{ (if Female).}$$

The central lab calculates the estimated creatinine clearance (CrCl) based on the following Cockcroft-Gault formula:

$$\text{CrCl (mL/min)} = [(140 - \text{age}) \times (\text{weight in kg}) \times (0.85 \text{ if female})] / [\text{serum creatinine (mg/dL)} \times 72].$$

11.3.2 Statistical Methods

The baseline value for clinical laboratory tests will be the last available measurement on or before the day of the first dose of study drug. Values on Day 1 must also be before the time of first dose if time is available. The same baseline value will be used for change to Treatment Period visits and change to Post-Treatment Period visits.

Mean changes from baseline to each post-baseline visit, including applicable post-treatment visits, will be summarized for each treatment arm. Each protocol-specified laboratory parameter will be summarized with the sample size, baseline mean, visit mean, change from baseline mean, standard deviation, minimum, median, and maximum.

Scatterplots of baseline versus final treatment visit for each hematology and chemistry parameter (specified in [Table 9](#)) and plots of the mean change in bilirubin (total, direct and indirect) from baseline to each treatment visit by treatment arm will be produced.

The laboratory parameters defined in [Table 9](#) will be assigned a toxicity grade of 1, 2, 3, or 4. The number and percentage of subjects with a maximum toxicity post-baseline grade of 1, 2, 3 or 4 will be summarized for each treatment arm. The maximum post-baseline value must be in a toxicity grade that is more extreme than the toxicity grade corresponding to the baseline value to be counted. The summary will also include the number and percentage of subjects with a maximum of at least Grade 3 for all laboratory parameters in [Table 9](#). Comparisons of the percentage of subjects experiencing a value meeting at least Grade 2 between treatment arms will be performed using Fisher's exact tests. Only P values ≤ 0.100 when rounded to three digits will be presented. A listing of all relevant laboratory parameters will be provided for each subject who had an increase to Grade 2 or higher value for any laboratory variable in [Table 9](#).

For ALT and total bilirubin, shift tables from baseline to maximum value in toxicity grade ([Table 9](#)) during the treatment period will be created. The shift tables will cross tabulate the frequency of subjects with baseline grade (0, 1, 2, 3, or 4) versus post-baseline

maximum grade (0, 1, 2, 3, or 4). Laboratory values of ALT and total bilirubin within normal ranges are defined as Grade 0.

Table 9. Definitions of Toxicity Grades 1, 2, 3, and 4 for Laboratory Values

| Test | Grade 1 | Grade 2 | Grade 3 | Grade 4 |
|---------------------------|-----------------------------------|------------------------------------|------------------------------------|-----------------------------|
| ALT/SGPT | > ULN – 3 × ULN | > 3 – 5 × ULN | > 5 – 20 × ULN | > 20 × ULN |
| AST/SGOT | > ULN – 3 × ULN | > 3 – 5 × ULN | > 5 – 20 × ULN | > 20 × ULN |
| Alkaline Phosphatase | > ULN – 2.5 × ULN | > 2.5 – 5 × ULN | > 5 – 20 × ULN | > 20 × ULN |
| GGT | > ULN – 2.5 × ULN | > 2.5 – 5 × ULN | > 5 – 20 × ULN | > 20 × ULN |
| Total Bilirubin | > ULN – 1.5 × ULN | > 1.5 – 3 × ULN | > 3 – 10 × ULN | > 10 × ULN |
| Hemoglobin | < LLN – 100 g/L | < 100 – 80 g/L | < 80 g/L | -- |
| White blood cells | < LLN – 3.0 × 10 ⁹ /L | < 3.0 – 2.0 × 10 ⁹ /L | < 2.0 – 1.0 × 10 ⁹ /L | < 1.0 × 10 ⁹ /L |
| Absolute Neutrophil Count | < LLN – 1.5 × 10 ⁹ /L | < 1.5 – 1.0 × 10 ⁹ /L | < 1.0 – 0.5 × 10 ⁹ /L | < 0.5 × 10 ⁹ /L |
| Platelet count | < LLN – 75.0 × 10 ⁹ /L | < 75.0 – 50.0 × 10 ⁹ /L | < 50.0 – 25.0 × 10 ⁹ /L | < 25.0 × 10 ⁹ /L |
| INR | > 1 – 1.5 × ULN | > 1.5 – 2.5 × ULN | > 2.5 × ULN | -- |
| Glucose (increased) | > ULN – 8.9 mmol/L | > 8.9 – 13.9 mmol/L | > 13.9 – 27.8 mmol/L | > 27.8 mmol/L |
| Glucose (decreased) | < LLN – 3.0 mmol/L | < 3.0 – 2.2 mmol/L | < 2.2 – 1.7 mmol/L | < 1.7 mmol/L |
| Creatinine | > ULN – 1.5 × ULN | > 1.5 – 3 × ULN | > 3 – 6 × ULN | > 6 × ULN |
| Creatinine clearance | < LLN – 60 mL/min | < 60 – 30 mL/min | < 30 – 15 mL/min | < 15 mL/min |
| Cholesterol | > ULN – 7.75 mmol/L | > 7.75 – 10.34 mmol/L | > 10.34 – 12.92 mmol/L | > 12.92 mmol/L |
| Albumin | < LLN – 30 g/L | < 30 – 20 g/L | < 20 g/L | -- |

Assessment of Liver Safety

The number and percentage of subjects in each treatment arm with maximum on-treatment lab values meeting the following criteria will be summarized:

- $ALT \geq 3 \times ULN$ and total bilirubin $\geq 2 \times ULN$;
- $ALT \geq 3 \times ULN$ and total bilirubin $< 2 \times ULN$;
- $ALT > 5 \times ULN$ and total bilirubin $< 2 \times ULN$;
- $ALT < 3 \times ULN$ and total bilirubin $\geq 2 \times ULN$.

The maximum post baseline ratio relative to the ULN will be used to determine if subjects meet the criteria listed above. The ALT and total bilirubin values do not need to be concurrent in order to meet the defined criteria. For ALT and total bilirubin, a subject will be counted if the post-baseline laboratory value meets the above criteria regardless of the baseline laboratory value (i.e., the post-baseline laboratory value does not need to be worse than the baseline laboratory value).

A listing of all ALT, AST, total, indirect and direct bilirubin, ratio of direct to total bilirubin, and alkaline phosphatase values will be provided for each subject who met any of the criteria defined above. The listings will be reviewed to assess bilirubin (e.g., mixed or direct predominance) and temporal relationships for subjects with $ALT \geq 3 \times ULN$ and total bilirubin $\geq 2 \times ULN$.

The number and percentage of subjects with post-baseline values during the Treatment Period meeting the following criteria will be summarized:

- $ALT > 5 \times ULN$ and $\geq 2 \times$ baseline;
- $AST > 5 \times ULN$ and $\geq 2 \times$ baseline;
- Total bilirubin $\geq 2.0 \times ULN$ and $>$ baseline.

As noted above, a post-baseline value must be more extreme than the baseline value to be considered. A separate listing will be provided that presents all lab values for the subjects meeting any of these criteria during treatment.

Laboratory Variables by Subgroups

Laboratory abnormalities of special interest will be assessed for the subgroups defined below:

- Sex (male, female)
- Age (< 65 years, ≥ 65 – < 75 years, ≥ 75 years)
- BMI (< 25, ≥ 25 kg/m²)
- Baseline fibrosis stage (F0 – F1, F2, F3, F4 (if applicable))
- Concomitant use of Calcium Channel Blockers (CCBs) (yes/no)

These subgroup analyses will be presented for the summary of ALT, AST, alkaline phosphatase, total bilirubin, and hemoglobin by maximum CTCAE grade.

Subgroup analyses will be presented by treatment arm and the Breslow-Day test will be used to examine the homogeneity of treatment effect across subgroups for the percentage of subjects with at least a Grade 2 abnormality and the percentage of subjects with at least a Grade 3 abnormality.

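### The joint liver screen and its review group are defined on ALT alone, so no output pairs raised AST with raised bilirubin

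*SAP*

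**What the plan says.** Under Assessment of Liver Safety, SAP Section 11.3.2 tabulates four joint categories of maximum on-treatment values:

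1. ALT at least 3 × ULN, total bilirubin at least 2 × ULN
2. ALT at least 3 × ULN, total bilirubin below 2 × ULN
3. ALT above 5 × ULN, total bilirubin below 2 × ULN
4. ALT below 3 × ULN, total bilirubin at least 2 × ULN

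The rule for assigning subjects is "The maximum post baseline ratio relative to the ULN will be used to determine if subjects meet the criteria listed above", and timing is set aside: "The ALT and total bilirubin values do not need to be concurrent in order to meet the defined criteria". ALT and bilirubin count whatever their baseline values were.

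For subjects meeting any of the four criteria, "A listing of all ALT, AST, total, indirect and direct bilirubin, ratio of direct to total bilirubin, and alkaline phosphatase values will be provided". The review itself is narrower. The SAP states: "The listings will be reviewed to assess bilirubin (e.g., mixed or direct predominance) and temporal relationships for subjects with" category 1 values, that is, ALT at least 3 × ULN and bilirubin at least 2 × ULN.

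AST appears elsewhere in the same section. Table 9 grades it with the same limits as ALT, and a separate count takes AST above 5 × ULN that is also at least twice baseline.

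**The concern.** The joint table is the only place where the SAP looks at a transaminase and bilirubin together, and its first category is the only one whose subjects are named for review. Because AST is absent, category 4 holds two kinds of subject: those with raised bilirubin and unremarkable transaminases, and those with raised bilirubin and clearly raised AST whose ALT happened to stay below 3 × ULN. The second kind has the combination that a joint screen would be expected to bring forward, yet nothing in the rules does so.

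Safety is part of the primary objectives (Section 4.1), and the arms are small (80 and 40 planned, Section 4.2). A reader who sees zero in category 1 may take it to mean that no subject had a raised transaminase with raised bilirubin. As written, it means only that no subject had raised ALT with raised bilirubin.

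**Working it through.** There is no power or sample size figure to reproduce here. The check is to apply the criteria as written to example profiles. The profiles are assumptions chosen to test the rules; they are not trial data.

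**Inputs (all SAP Section 11.3.2).** The four joint categories above; the separate AST rule (above 5 × ULN and at least 2 × baseline); the Table 9 AST grades (Grade 2 is above 3 to 5 × ULN, Grade 3 is above 5 to 20 × ULN); and the requirement that a graded value be in a worse grade than baseline to be counted.

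**Step 1: classify as written, then test the proposed extra row**, which is met when max(ALT, AST) ≥ 3 and bilirubin ≥ 2. All values are maxima in multiples of ULN, except for the baseline column.

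| ALT | AST | Bilirubin | AST baseline | Joint category as written | Separate AST rule | Extra row met |
|---|---|---|---|---|---|---|
| 2.5 | 4 | 2.5 | 1 | 4, not reviewed | No (4 is not above 5) | Yes |
| 2.5 | 8 | 2.5 | 1 | 4, not reviewed | Yes (8/1 = 8) | Yes |
| 2.9 | 8 | 2.0 | 5 | 4, not reviewed | No (8/5 = 1.6, below 2) | Yes |
| 4 | 8 | 2.5 | 1 | 1, reviewed | Yes (8/1 = 8) | Yes |
| 1 | 1 | 2.5 | 1 | 4, not reviewed | No | No |

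The first three profiles fall in the same row as the last, which has no transaminase rise. The extra row picks out the first three and leaves the last where it is, so a pure bilirubin rise remains distinguishable. The fourth profile shows the limit of the problem: once maximum ALT reaches 3 × ULN, the subject is reviewed however high AST is.

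**Step 2: see what the other AST outputs catch.** In the first profile AST rises from Grade 0 to Grade 2, so it enters the Table 9 summary and the listing of increases to Grade 2 or higher. In the third, a baseline of exactly 5 × ULN is Grade 2 and the maximum of 8 × ULN is Grade 3, so it is counted by grade. Move that baseline to 5.1 × ULN and both values are Grade 3, so there is no grade count; and 8/5.1 = 1.57, so the separate AST rule fails as well. That subject meets no AST threshold count at all. The joint categories, by contrast, ignore baseline.

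**Step 3: size.** One subject is 1/80 = 1.25% of Arm A or 1/40 = 2.5% of Arm B. This is the weight of any single subject in any table. How many subjects would have this pattern cannot be derived from the SAP.

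**The case against.** The case for leaving the plan alone has real force.

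- **No case disappears.** Category 4 subjects are listed with AST, bilirubin fractions and alkaline phosphatase. If bilirubin exceeds its baseline, they are also counted under the separate bilirubin rule, with a listing of all laboratory values. Events of hepatic decompensation and failure are searched for separately (Section 11.2.2). This stands, and it rules out saying that such cases are missed altogether.
- **AST between 3 and 5 × ULN is not ignored.** A reader who looks only at the liver-safety bullets might infer that it meets no transaminase criterion. Table 9, in the same section, makes values above 3 × ULN Grade 2, with a count, a between-arm Fisher test at Grade 2 or higher and a listing, provided the grade rose from baseline.
- **The ALT focus is not an internal contradiction.** A reader might infer that the SAP treats AST and ALT alike everywhere else. It does not: the shift tables cover ALT and total bilirubin only. Section 12.1 also says that the safety analyses were aligned across the program.
- **The table is descriptive.** No test or decision rule rests on it, and the SAP does not label category 4 as isolated bilirubin elevation or category 1 as suspected drug injury.
- **AST is less specific to the liver than ALT**, so adding it may bring in non-hepatic rises.

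These points reduce the priority. They do not supply what is absent: a count that joins AST to bilirubin, or a rule that brings such a subject into the review. The listing shows the values, but the SAP directs the review only to category 1.

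**Conclusion.** The point holds as a minor weakness in how the screen is fixed. It is confined to subjects with maximum ALT below 3 × ULN, AST at or above 3 × ULN and bilirubin at or above 2 × ULN. Within the joint table they appear only in category 4, mixed with subjects who have normal transaminases, and they are outside the named review. The AST counts elsewhere depend on baseline and do not consider bilirubin.

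The affected number is unknown and probably low; that is a judgement, since the SAP gives no frequency. The conclusion assumes that the review will follow the SAP wording and not be widened informally when the category 4 listing is read. It does not support a claim that AST-dominant injury in general escapes the plan, or that the SAP contradicts itself.

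**What to change.** In Section 11.3.2:

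- Keep the four ALT-based rows unchanged, so that results stay comparable across the program.
- Add one row: ALT or AST at least 3 × ULN with total bilirubin at least 2 × ULN, using the larger of the two maximum ratios to ULN.
- State that the existing rules on concurrency and on disregarding baseline apply to AST in this row.
- Extend the review of bilirubin pattern and timing, and the accompanying listing, to subjects in the new row.

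The cost is a few words and one derived variable from data already collected. The downside is that a few subjects with non-hepatic AST rises may enter the review; the retained ALT rows show how many were added because of AST.

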11.4 Analysis of Vital Signs and Weight

11.4.1 Variables and Criteria Defining Abnormality

Vital sign variables are body temperature, sitting systolic blood pressure, sitting diastolic blood pressure, sitting pulse rate, and body weight.

The criteria for potentially clinically significant vital sign findings are presented in [Table 10](#).

Table 10. Criteria for Potentially Clinically Significant Vital Sign Values

| Test/Measurement | Very Low (VL) | Very High (VH) |
|--------------------------|---|--|
| Systolic Blood Pressure | ≤ 90 mmHg AND A decrease of ≥ 20 mmHg from baseline | ≥ 180 mmHg AND An increase of ≥ 20 mmHg from baseline |
| Diastolic Blood Pressure | ≤ 50 mmHg AND A decrease of ≥ 15 mmHg from baseline | ≥ 105 mmHg AND An increase of ≥ 15 mmHg from baseline |
| Pulse Rate | ≤ 50 bpm AND A decrease of ≥ 15 bpm from baseline | ≥ 120 bpm AND An increase of ≥ 15 bpm from baseline |
| Weight | A decrease of $\geq 15\%$ from baseline | An increase of $\geq 15\%$ from baseline |
| Body Temperature | | $> 38.3^{\circ}\text{C}$ AND An increase of $\geq 1.1^{\circ}\text{C}$ from baseline |

11.4.2 Statistical Methods

The baseline value for vital signs will be the last measurement on or before the day of the first dose of study drug. The same baseline value will be used for change to Treatment Period visits and change to Post-Treatment Period visits.

Mean changes from baseline to each post-baseline visit, including applicable post-treatment visits, will be summarized for each treatment arm. Each vital sign parameter will be summarized with the baseline mean, visit mean, change from baseline mean, standard deviation, minimum, median, and maximum.

The number and percentage of subjects with on-treatment values meeting the specified criteria for Potentially Clinically Significant (PCS) vital sign values (Table 10) will be summarized for each treatment arm. A post-baseline value must be more extreme than the baseline value to be considered a PCS finding. A separate listing will be provided that presents all vital sign values for the subjects meeting PCS criteria during treatment.

12.0 Summary of Changes

12.1 Summary of Changes Between the Latest Version of the Protocol and SAP

- Added unplanned interim analysis when all subjects reach PT Week 4 or prematurely discontinue from the study to allow for the submission to the PMDA at the time of SVR₄ analysis.
- Added secondary analyses, sensitivity analyses, subgroup analyses, and additional analyses for the submission to the PMDA at the time of SVR₄ analysis.
- Updates were made to the resistance analysis plan to be consistent across the HCV ABT-493/ABT-530 program;
- Updated safety analyses to align across the HCV ABT-493/ABT-530 program;
- Added additional summaries of demographics, baseline characteristics to provide geographic region-specific information (Section 7.1).

